Although the literature on economical and psychosocial impact of disasters is growing, we have very little empirical data to guide ACP with our sickest patients during a disaster. Via this new research, we seek to learn whether a disaster would make patients with a serious chronic illness more or less likely to want aggressive treatment. We posit that the effects of a disaster bring doubt to clinicians as well as families regarding how to interpret an advance directive or end-of-life care preferences expressed some time ago before the pandemic. We will generate empirical data on the impact of the COVID-19 pandemic on patients' end-of-life preferences, to address whether the stability of preferences is disrupted by the pandemic, and to identify patient characteristics, including race/ethnicity, associated with pre-/post-pandemic changes.

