 - 5) The proportion of decisions made at 6 months (e.g. stopping dialysis, DNR order, and hospice enrollment etc.) follow-up or death of patient will be higher in the intervention dyads than that of control dyads.
- Aim 2:
 - 1) HAD-anxiety scores in SPIRIT surrogates will be lower than those of control surrogates at 1 month after the patient's death.
 - 2) HAD-depression scores in SPIRIT surrogates will be lower than those of control surrogates at 1 months after the patient's death.

Supplement cohort study:

Aim 1. Changes in patient's goals of care preferences over time (T2-T3 and T2-T4) in the intervention group will be smaller than those in the control group.

Aim 2. Changes in the preparedness outcomes over time in the intervention group will be smaller than those in the control group.

Aim 3. The COVID-19 Related Stress and race/ethnicity will be significantly associated with changes in goals of care stability and the preparedness outcomes.

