Due to the exploratory nature of the study, a traditional sample size calculation was not performed. Instead, our goal was to provide estimates of effect sizes (standardized mean differences between pre- and during- COVID-19 study points) for the outcomes in aims 1-3. Preliminary power calculations based on a two-sample t-test, indicate that a sample size of 72 in the SPIRIT intervention and 35 in the usual care group achieve 80% power to detect a difference in mean changes of 0.5 between the groups. This calculation assumes a repeated measures design with a standard deviation of 1.0 at both time points, a between measurement correlation of 0.2 and a 5% significance level.

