Aim 1. Compare the stability of patients’ goals-of-care preferences over time, from pre-outbreak to during-outbreak, by group and estimate effect by race: We will use mixed effects modeling to assess differences in patients’ goals of care over time, from pre- to post-lockdown time points. We will sequentially build a longitudinal model that will include time, treatment group and race as fixed effects; then 2-way interactions of time x group, time x race, treatment x race, and finally a 3-way interaction of time x group x race, if the sample size permits. We will select the most parsimonious model using Akaike information criterion (AIC) and Bayesian information criterion (BIC). We will use contrasts to test whether participants demonstrated significant change in goals-of-care preferences across different combinations of treatment and race.

Aim 2. Assess the stability in the three preparedness outcomes, from pre-outbreak to during-outbreak by group, and estimate race effect: We will perform analyses similar to those described in Aim 1. In addition, for non-normal outcomes (binary, count) a generalized mixed effects model will be used. Appropriate contrasts will be used to assess differences in the outcomes over time by treatment groups, race and groups x race.

Aim 3. Examining the associations of the COVID-19 Related Stress, sex, race/ethnicity, and other sociodemographic characteristics to the level of changes in the preparedness outcomes and patient’s goals-of-care preference stability: We will use analysis of covariance to assess the relationship between COVID-19 related stress and changes in outcomes from T2 to T3 and T3 to T4, after controlling for the corresponding baseline values of the outcomes (i.e., T2 and T3 respectively). Using similar methods, we will evaluate whether there are disparate effects of sex, race/ethnicity and other sociodemographic factors on outcome changes and goals-of-care preference stability from T2 to T3 and T3 to T4, respectively

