9.4.7 SUB-GROUP ANALYSES

In order to evaluate whether the SPIRIT has differential effects according to demographic factors such as age, sex, race/ethnicity we consider the same generalized mixed effects model in the context of protocol design, mentioned in Section 9.4.1. Our approach is first to consider each factor one at a time. We will fit the same generalized mixed model by additionally including a subject level factor (e.g., race) and its' interaction with the SPIRIT. If the interaction is significant the analysis will indicate that SPIRIT effect changes according to race. We will report p-values and importantly, standard errors and confidence intervals by recognizing the fact that we may not have power to detect significant interaction effects for examining all demographic factor combinations.

For Supplement Aims: no subgroup analyses will be possible due to the small sample size.

Supplement cohort study: no subgroup analyses will be possible due to the small sample size

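### The COVID-19 cohort tests for significant change across arm-by-race combinations and gives no other criterion for stability; with arms of 72 and 35, comparing arms by significance would be distorted by size alone

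*Combined protocol and SAP*

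**What the plan says.** Section 2.2 gives the purpose of the supplement cohort: "to address whether the stability of preferences is disrupted by the pandemic".

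Section 9.1 states two between-arm hypotheses. The one on goals-of-care preferences reads: "Changes in patient's goals of care preferences over time (T2-T3 and T2-T4) in the intervention group will be smaller than those in the control group". A parallel hypothesis under Aim 2 has the same form and covers preparedness.

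Section 9.2 calls the cohort exploratory, gives effect-size estimation as its goal, and bases its power statement on "a sample size of 72 in the SPIRIT intervention and 35 in the usual care group". The inputs are a difference of 0.5 in mean change, an SD of 1.0 at each time point and a correlation of 0.2.

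For Aim 1, section 9.4.2 builds a mixed model in steps: main effects of time, group and race, then the two-way interactions, and "finally a 3-way interaction of time x group x race, if the sample size permits". AIC and BIC choose the most parsimonious model. The inferential step follows: "We will use contrasts to test whether participants demonstrated significant change in goals-of-care preferences across different combinations of treatment and race". The analysis for Aim 2 is similar: "Appropriate contrasts will be used to assess differences in the outcomes over time by treatment groups, race and groups x race".

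Section 9.4.7 says: "Supplement cohort study: no subgroup analyses will be possible due to the small sample size".

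No section gives a numerical definition of stable, an equivalence test, or a rule for reading a non-significant contrast.

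**The concern.** Showing that preferences were stable requires evidence that change was small. A test for significant change cannot supply that, because a small group can fail to reach significance whatever the true change. The usual-care arm is about half the size of the SPIRIT arm (35/72 = 0.49). If the contrasts are read arm by arm, the same true change is more likely to be declared in SPIRIT and overlooked in usual care. That pattern would contradict the hypothesis that SPIRIT dyads change less, and it would come from arm size only.

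Two features of the plan make this more than a matter of wording. First, model selection by AIC and BIC may drop time x group, the term that carries the 9.1 hypotheses. Second, 9.4.2 plans contrasts over treatment-by-race combinations while 9.4.7 says the sample cannot support subgroup analyses.

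At stake is what the cohort can conclude about relying on preferences stated before the pandemic, and about whether SPIRIT protects their stability.

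**Working it through.** **Inputs (9.2, cohort paragraph).** n = 72 (SPIRIT) and 35 (usual care); SD 1.0 at both times; correlation 0.2; planning difference 0.5; 5% level. The number of sides is not stated; two-sided is assumed here. Dyads are treated as independent, as in the t-test that 9.2 names.

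**SD of a change score.** sqrt(2 × (1 − 0.2)) × 1.0 = sqrt(1.6) = 1.265.

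**The plan's own figure (80% power, between-arm difference of 0.5).**
- Standard error of the difference = 1.265 × sqrt(1/72 + 1/35) = 0.261.
- Noncentrality = 0.5 / 0.261 = 1.92; critical t on 105 df = 1.98.
- Power (noncentral t) = about 48% two-sided, 60% one-sided.

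The stated 80% is not reproduced by the test described. Two-sided, it would need a correlation of about 0.63. A one-sided ANCOVA, with SD sqrt(1 − 0.2²) = 0.98, comes close at 79%, but that is not the test described. The expected 95% CI half-width for the between-arm difference is 1.98 × 0.261 = 0.52.

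**Change within one arm, true change 0.5.** One-sample t-test, two-sided 5%:

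| Arm | n | SE = 1.265/√n | Noncentrality | Power | Missed | 95% CI half-width |
|---|---|---|---|---|---|---|
| SPIRIT | 72 | 0.149 | 3.35 | 0.911 | 9% | 0.30 |
| Usual care | 35 | 0.214 | 2.34 | 0.623 | 38% | 0.43 |

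**Discordant results when both arms truly change by 0.5.**
- SPIRIT significant, usual care not: 0.9112 × (1 − 0.6226) = 0.344, about 34%.
- Usual care significant, SPIRIT not: 0.6226 × (1 − 0.9112) = 0.055, about 6%.

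The true difference in change is zero in both cases.

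**Would a stability margin of 0.5 solve it?** Suppose an arm is called stable only if its 95% CI lies within ±0.5. With zero true change in both arms, simulation on the same inputs calls SPIRIT stable about 82% of the time and usual care about a quarter of the time. SPIRIT alone would be called stable about 61% of the time, usual care alone about 4–5%. The size artefact returns, now in favour of the cohort's hypothesis. The 0.5 in 9.2 is also a planning difference between arms, not a judgement about how much within-arm change is tolerable.

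**Race.** The documents give no race counts for the cohort, so no miss rates are calculated for arm-by-race cells.

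**The case against.** A reader might infer that the plan defines stable as p > 0.05 within each arm-by-race cell. The documents do not say so. The 9.1 hypotheses are between-arm, 9.2 powers a between-arm difference, and time x group and time x race are already in the model sequence. The contrast sentence can also be read as comparing combinations with one another, and the Aim 2 wording leans that way. A hypothesis of difference needs no margin. All of this stands, and it limits the point to a missing criterion and an open reading.

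A reader might also infer that the smaller race group within an arm will look stable for lack of data. This is not supported. Race counts are absent, the three-way term is conditional on sample size and may not survive AIC/BIC, and without it the cells share information within one model. Separate one-sample tests per cell do not represent that analysis.

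Finally, the distortion by arm size runs against the cohort's own hypothesis, and the cohort is exploratory. That lowers the stakes but leaves three gaps: the stated inferential step is a test of significant change, the term carrying the hypotheses can be dropped, and 9.4.2 and 9.4.7 disagree.

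**Conclusion.** The point holds in a limited form. For cohort Aims 1 and 2 the plan offers contrasts testing for change and no other criterion for stability, while its hypotheses concern the between-arm difference in change and 9.4.7 excludes subgroup analyses. If arms are compared by which one shows significant change, unequal size alone yields SPIRIT-only significance about 34% of the time against about 6% for the reverse, when both arms change by 0.5.

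These figures rest on the SD and correlation in 9.2, a two-sided 5% test, independent dyads and an assumed true change of 0.5. The within-arm tests stand in for contrasts from the mixed model, so they illustrate the effect of arm size and do not predict the cohort's results. The SD of 1.0 is a planning scale. The Goals-of-Care Tool in 8.1 has three response options per scenario, so a mean change near zero could also hide patients switching in opposite directions.

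The change should be made because it affects what the cohort can conclude and costs almost nothing.

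**What to change.** In 9.4.2, cohort Aims 1 and 2:

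1. Keep time x group in the model regardless of AIC or BIC. Make the between-arm difference in change, with its 95% CI, the test of the 9.1 hypotheses.
2. Compare races only through the difference in change (time x race) with its CI, never by one group being significant and another not.
3. Report change within each arm as an estimate with a 95% CI, and state that a non-significant change is not evidence of stability.
4. Report arm-by-race combinations as estimates with CIs only, without significance verdicts, and reconcile this wording with 9.4.7.

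Do not adopt 0.5 as a stability margin.

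The cost is a few sentences of analysis-plan wording and no new data. The downside is that some within-arm results, especially in controls, will be reported as inconclusive. The between-arm estimate will also be imprecise, with a half-width of about 0.52 on the plan's inputs.

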9.4.3 ANALYSIS OF THE SECONDARY ENDPOINT(S)

Analysis of secondary endpoints are not dependent on findings of primary endpoints.

SPIRIT effectiveness on surrogates’ post-bereavement psychological distress: We will use the same approach as in the analysis of the primary endpoints to compare anxiety, depression, and post-traumatic distress symptoms in SPIRIT vs usual care among surrogates of patients who die during the initial implementation and 9-month (or extended) follow-up.

Implementation process outcomes: Quantitative data on acceptability, fidelity, and costs of SPIRIT will be summarized using descriptive statistics. SPIRIT will be determined to be acceptable to care providers and patients and surrogates if over 75% of responses exceed an average summative score ≥ 3 (of 4) on the acceptability measures. Cost estimates will be used to ascertain resources needed to implement or replicate SPIRIT in the

future.⁹² We will also explore the relationships of these quantitative data with characteristics of settings and stakeholders. Transcripts of acceptability interviews will be transferred to ATLAS.ti for analysis. Content analysis techniques⁹³ will be used without preconceived categories.⁹⁴ Open coding will be applied⁹⁵ and disagreements on coding will be resolved by consensus. We will examine the data for patterns or differences in themes between those with acceptability scores ≥ 3 and scores < 3 and setting characteristics. This analysis will be facilitated by creating matrixes that organize textual and numeric data for comparing and contrasting⁹⁶ so that what contributed to acceptability scores that are positive and less than positive may be identified. We will use a similar approach, content analysis, to evaluate the sustainability data.

9.4.4 SAFETY ANALYSES

Not applicable.

9.4.5 BASELINE DESCRIPTIVE STATISTICS

See 9.4.1 General Approach.

9.4.6 PLANNED INTERIM ANALYSES

Not applicable.

9.4.7 SUB-GROUP ANALYSES

In order to evaluate whether the SPIRIT has differential effects according to demographic factors such as age, sex, race/ethnicity we consider the same generalized mixed effects model in the context of protocol design, mentioned in Section 9.4.1. Our approach is first to consider each factor one at a time. We will fit the same generalized mixed model by additionally including a subject level factor (e.g., race) and its' interaction with the SPIRIT. If the interaction is significant the analysis will indicate that SPIRIT effect changes according to race. We will report p-values and importantly, standard errors and confidence intervals by recognizing the fact that we may not have power to detect significant interaction effects for examining all demographic factor combinations.

For Supplement Aims: no subgroup analyses will be possible due to the small sample size.

Supplement cohort study: no subgroup analyses will be possible due to the small sample size

9.4.8 TABULATION OF INDIVIDUAL PARTICIPANT DATA

Individual participant data will be listed by measure and time point.

9.4.9 EXPLORATORY ANALYSES

SPIRIT effectiveness on end-of-life treatment intensity: Among patients who die during the initial SPIRIT implementation and follow-up, percentages of patients hospitalized, having ICU admission, having intensive procedures and length of hospital stay in the final month of life will be summarized using descriptive statistics, 95% CIs, and graphical displays. The exploratory examination of SPIRIT's effectiveness on improving these outcomes, we will use the same analytic approach as in the analysis of the primary endpoints (See 9.4.2).

10 SUPPORTING DOCUMENTATION AND OPERATIONAL CONSIDERATIONS

10.1 REGULATORY, ETHICAL, AND STUDY OVERSIGHT CONSIDERATIONS

10.1.1 INFORMED CONSENT PROCESS

10.1.1.1 CONSENT/ASSENT AND OTHER INFORMATIONAL DOCUMENTS PROVIDED TO PARTICIPANTS

Consent forms describing in detail the study intervention, study procedures, and risks are given to the participant and written documentation of informed consent is required prior to starting intervention/administering study intervention. The following consent materials are submitted with this protocol.

- Patient Consent Form-SPIRIT
- Patient Consent Form-Usual Care
- Surrogate Verbal Consent Form –SPIRIT
- Surrogate Verbal Consent Form – Usual Care
- Care Provider Verbal Consent Form
- VERBAL Consent Addendum – Patient
- VERBAL Consent Addendum - Surrogate

For Supplement Aims, the following consent materials will be used:

- Patient Verbal Consent for Screening (cognitive impairment level)
- Patient Consent Form
- Surrogate Verbal Consent Form

Supplement cohort study:

- Verbal Consent Addendum for Cohort – Patient
- Verbal Consent Addendum for Cohort - Surrogate

10.1.1.2 CONSENT PROCEDURES AND DOCUMENTATION

Participating dialysis centers/clinics will be randomized first (see the study flow diagram). The care team member who has been selected by the clinic as a care provider responsible for SPIRIT delivery at each clinic in both groups (e.g., nurse or social worker) will generate a list of patients each quarter based on the inclusion criteria. This staff member may differ from clinic to clinic depending on who is qualified, comfortable and able to assess each potential participant. The medical director of the dialysis unit (and/or the attending physician as required) approves the list if required by the dialysis center. From this list, one of the care providers will then assess the patient's willingness to meet with a recruiter from the research team. The recruiter (e.g., site coordinator) will then approach willing patients during their scheduled dialysis clinic appointment.

Consent forms have been Institutional Review Board (IRB)-approved and the participant will be asked to read and review the document. In a private room, a verbal explanation will be provided in terms suited to the patient's comprehension of the purposes, procedures, and potential risks of the study and of their rights as research participants. Patient participants will have the opportunity to carefully review the written consent form (including HIPAA authorization form) and ask questions prior to signing. The patient participants should have the opportunity to discuss the study with their family or surrogates or think about it prior to agreeing to participate. The patient participant will sign the informed consent document prior to any procedures being done specifically for the study. Patient participants must be informed that participation is voluntary and that they may withdraw from the study at any time, without prejudice. A copy of the informed consent document will be given to the

participants for their records. The informed consent process will be conducted and documented in the source document (including the date), and the form signed, before the participant undergoes any study-specific procedures. The rights and welfare of the participants will be protected by emphasizing to them that the quality of their medical care will not be adversely affected if they decline to participate in this study. The recruiter will then provide the patient participant with a study brochure and encourage him/her to talk to the surrogate regarding the study within the next 2-3 days (to avoid a cold call).

Several days later, the recruiter will telephone the potential surrogate participant to assess his/her willingness to participate. Following the Surrogate Verbal Consent Form, a verbal explanation will be provided in terms suited to the surrogate's comprehension of the purposes, procedures, and potential risks of the study and of their rights as research participants. Upon the surrogate's verbal consent using the IRB approved script/form, the research staff at the Emory Study Coordination Center will schedule and conduct a baseline data collection session. All surrogates will provide verbal consent only with a waiver of written consent and a Surrogate Verbal Consent form will be signed by the recruiter.

For Supplement Aims:

Participants will be recruited from the Emory dialysis centers and UVA dialysis centers. First, patients who have been diagnosed with an early stage of dementia (mild to moderate) or are suspected of having cognitive impairment by a care provider will be referred by the dialysis APRN. The medical records of those patients will be reviewed to preliminarily determine eligibility by a research staff member. During the patient's dialysis treatment session at the center, the patient's care provider will gain permission for the staff member to explain the study. With the patient's permission, the staff member will approach the patient, briefly explain the study, obtain verbal consent to conduct the MOCA or SLUMS and UBACC screening. If the patient has met the criteria for both early stages of cognitive impairment and decision-making capacity, the research staff member will provide detailed study information and confirm his/her surrogate decision-maker. Written consent will then be obtained from the patient. The research staff member will obtain the name and phone number of the surrogate (or confirm with the medical record as necessary) and call the surrogate in 2-3 days to assess the surrogate's willingness to participate. Verbal consent will be obtained from the surrogate.

Supplement cohort study:

At the upcoming scheduled monthly check-in call with the participant (in the parent study, a check-in telephone call [scripted] is made to each member of the dyad after the 2-week follow-up call), the research staff member will proceed with the procedures for the parent study and then introduce the participant to the supplement study, including the purpose and procedures and obtain verbal consent. After both members of the dyad have consented, the recruiter will schedule two data collection calls (baseline/T3 and 6 months/T4).

10.1.2 STUDY DISCONTINUATION AND CLOSURE

It is very unlikely that this study may be suspended or prematurely terminated since the SPIRIT intervention has been extensively tested, including its safety and efficacy. Also, this study aim includes collecting implementation data and no planned interim analysis and stopping rules. Nonetheless, if suspension or termination occurs, written notification, documenting the reason for study suspension or termination, will be provided by the suspending or terminating party to study participants, investigator, dialysis organizations, and regulatory authorities. If the study is terminated or suspended, the Principal Investigator (PI) will promptly inform study participants, the Institutional Review Board (IRB), and sponsor and will provide the reason(s) for the termination or suspension. Study participants will be contacted, as applicable, and be informed of changes to study appointment schedule.

Circumstances that may warrant termination or suspension include, but are not limited to:

- Determination of unexpected, significant, or unacceptable risk to participants
- Insufficient compliance to protocol requirements

Study may resume once concerns about safety, protocol compliance, and data quality are addressed, and satisfy the sponsor and IRB.

